### 6.2.2 PERIOD 2 (+ 24 weeks [optionally up to a maximum 12 months of P2Y12 inhibitor treatment after ACS underwent PCI, based on investigator's discretion])

#### 6.2.2.1 Primary Endpoint

The primary endpoint will be the incidence of major bleeding events (non-coronary artery bypass grafting [CABG] thrombolysis in myocardial infarction (TIMI) major) after 28 MD treatment weeks or up to maximum 12-month P2Y12 inhibitor treatment after ACS underwent PCI.

#### 6.2.2.2 Secondary Endpoint(s)

Safety: Incidence of:

- Minor and clinically relevant bleeding events after 28 MD treatment weeks or up to maximum 12-month P2Y12 inhibitor treatment after ACS underwent PCI
- Major adverse cardiovascular events (MACE) including cardiovascular death, non-fatal myocardial infarction (MI), non-fatal stroke, stent thrombosis and revascularization after 28 MD treatment weeks, or up to maximum 12-month P2Y12 inhibitor treatment after ACS underwent PCI

- All cause deaths after 28 MD treatment weeks or up to maximum 12-month P2Y12 inhibitor treatment after ACS underwent PCI)
- Adverse events after 28 MD treatment weeks or up to maximum 12-month P2Y12 inhibitor treatment after ACS underwent PCI)

### 6.2.3 Exploratory Endpoint(s)

The association CYP2C19 genotyping for available subjects (targeted 100 subjects) who have signed the pharmacogenomic informed consent form separately.

## 7.0 Investigational Plan

### 7.1 Overall Study Design and Plan: Description

This phase 4 study is designed as multicenter, non-comparative, open label, 28-week (optionally up to a maximum 12 months of P2Y12 inhibitor treatment after ACS underwent PCI, based on investigator's discretion) switching study in subjects with a previous diagnosis of Acute Coronary Syndrome (ACS) who had underwent Percutaneous Coronary Intervention (PCI) and were treated with either (a) clopidogrel maintenance dose (MD) of 75 mg once daily and aspirin 81-100 mg per day for 2-8 weeks following clopidogrel loading dose (LD) of 300 mg or 600 mg at the time of PCI; or (b) ticagrelor MD of 90 mg bid and aspirin 81-100 mg per day for 1-4 weeks and switching to clopidogrel maintenance dose (MD) of 75 mg once daily and aspirin 81-100 mg per day for 2-4 weeks (either directly or via clopidogrel loading dose [LD] of 300 mg or 600 mg) following ticagrelor LD of 180 mg at the time of PCI; or (c) clopidogrel maintenance dose (MD) of 75 mg once daily and aspirin 81-100 mg per day for 2-8 weeks following ticagrelor LD of 180 mg at the time of PCI; or (d) based on investigator's judgement with at least 2 weeks continues use of clopidogrel MD and aspirin 81-100 mg per day before switching to prasugrel and maximum 8 weeks P2Y12 inhibitors MD treatment (prasugrel is not allowed).

[figure not shown]
Eligible subjects will receive open-label prasugrel MD 3.75 mg once daily and aspirin 81-100 mg per day. The investigator's discretion will be followed for deciding on aspirin dosing as far as continuing the dual antiplatelet therapy (DAPT) may increase the risk of gastrointestinal bleeding; therefore adverse events management related to aspirin doses will be managed as per the investigator's criteria for this and any other criteria based on medical judgement.

After signing the study informed consent, subjects will enter a flexible screening period based on the investigator's discretion (lasting up to a maximum of 4 weeks). Key inclusion / exclusion criteria will be verified to determine subject eligibility at the screening.

There is Period 1 of 4-week prasugrel MD treatment period, starting on Day 1, followed by a Period 2 of +24-week prasugrel MD treatment (optionally up to a maximum 12 months of P2Y12 inhibitor treatment after ACS underwent PCI), and thereafter a safety follow-up for patients with AEs at the last treatment. For early termination, all the assessments of the treatment week 28 visit (optionally up to a maximum 12 months of P2Y12 inhibitor treatment after ACS underwent PCI, based on investigator's discretion) should be performed, if possible, including the safety follow-up for AEs at the last treatment.

A schematic of the study design is included in [Figure 1](#) and the schedule of assessments is listed in [Appendix 18.1](#).

Figure 1. Study figure

## 7.2. Discussion of Study Design, including the Choice of Control Groups

This trial is designed as a phase 4, multicenter, non-comparative, open label, 28 weeks (optionally up to a maximum 12 months of P2Y12 inhibitor treatment after ACS underwent PCI) switching study in subjects with a previous diagnosis of Acute Coronary Syndrome (ACS) who had undergone Percutaneous Coronary Intervention (PCI) and were treated with either (a) clopidogrel maintenance dose (MD) of 75 mg once daily and aspirin 81-100 mg per day for 2-8 weeks following clopidogrel loading dose (LD) of 300 mg or 600 mg at the time of PCI; or (b) ticagrelor MD of 90 mg bid and aspirin 81-100 mg per day for 1-4 weeks and switching to clopidogrel maintenance dose (MD) of 75 mg once daily and aspirin 81-100 mg per day for 2-4 weeks (either directly or via clopidogrel loading dose [LD] of 300 mg or 600 mg) following ticagrelor LD of 180 mg at the time of PCI; or (c) clopidogrel maintenance dose (MD) of 75 mg once daily and aspirin 81-100 mg per day for 2-8 weeks following ticagrelor LD of 180 mg at the time of PCI; or (d) based on investigator's judgement with at least 2 weeks continues use of clopidogrel MD and aspirin 81-100 mg per day before switching to prasugrel and maximum 8 weeks P2Y12 inhibitors MD treatment (prasugrel is not allowed).

The prasugrel MD dose for this study (3.75 mg once daily) has been selected based on the package insert DSTW 201803-03, Daiichi Sankyo Taiwan Ltd. The investigator's discretion will be followed for deciding on aspirin dosing as far as continuing the dual antiplatelet therapy (DAPT) may increase the risk of gastrointestinal bleeding; therefore adverse events management related to aspirin doses will be managed as per the investigator's criteria for this and any other criteria based on medical judgement.

The P2Y12 reaction unit (PRU) assessed with VerifyNow® has been selected for the evaluation of the study primary endpoint because this is one of the most user-friendly point-of-care (POC) platelet function test systems because it produces rapid results at the patient bed-site, and the VerifyNow platform consists on a validated tool which has currently three types of single-use,

disposable cartridges that can be used to monitor different antiplatelet drugs: aspirin, clopidogrel and glycoprotein (GP) IIb/IIIa therapy. The PRU will be assessed immediately before dosing as that will assess the steady state which is the most appropriate approach for a maintenance dose. For clopidogrel assessment, Day 1 (before prasugrel switch dosing) is selected as being the last day of clopidogrel 75 MD after 4 weeks screening (suggested test timing for clopidogrel 75 mg  $\geq$  6 days of maintenance). For prasugrel assessment, Week 4 is selected as being the last day of prasugrel 3.75 mg MD after 4 weeks treatment Period 1 (suggested test timing for prasugrel 5 mg  $\geq$  5 days on maintenance).

The study has been designed with 2 periods: the first one to assess the platelet function after 4 weeks, and a longer period up to 28 weeks for a mid-term safety assessment of bleeding events, major adverse cardiovascular events (MACE), and all cause deaths. Based on the investigator's discretion, patients will be offered to extend Period 2 up to maximum 12 months of P2Y12 inhibitor treatment after ACS underwent PCI for an additional safety assessment of the same objectives.

The study sample size is based on the expected PRU change from baseline after 4 weeks of treatment based on a previously published reference. We consider the antiplatelet effect of prasugrel in PRU value assessed with VerifyNow® can be observed within 4 weeks which is a valid recall period, assessing other safety endpoints during a longer Period 2 (+24 weeks; or optionally up to a maximum 12 months of P2Y12 inhibitor treatment after ACS underwent PCI based on investigator's discretion). The selected sample size will be also enough for an 82% probability that 1 or more adverse reactions (or other events) will occur with an anticipated incidence close to 0.01.

## 8.0 Selection of study Population

The subject population will comprise male and female subjects of any race, aged at least 20 years at screening, with a previous diagnosis of ACS, NSTEMI, STEMI or UA, a weight of at least 50 Kg at the time of screening, and having undergone PCI and previously treated with either (a) clopidogrel maintenance dose (MD) of 75 mg once daily and aspirin 81-100 mg per day for 2-8 weeks following clopidogrel loading dose (LD) of 300 mg or 600 mg at the time of PCI; or (b) ticagrelor MD of 90 mg bid and aspirin 81-100 mg per day for 1-4 weeks and switching to clopidogrel maintenance dose (MD) of 75 mg once daily and aspirin 81-100 mg per day for 2-4 weeks (either directly or via clopidogrel loading dose [LD] of 300 mg or 600 mg) following ticagrelor LD of 180 mg at the time of PCI; or (c) clopidogrel maintenance dose (MD) of 75 mg once daily and aspirin 81-100 mg per day for 2-8 weeks following ticagrelor LD of 180 mg at the time of PCI; or (d) based on investigator's judgement with at least 2 weeks continuous use of clopidogrel MD and aspirin 81-100 mg per day before switching to prasugrel and maximum 8 weeks P2Y12 inhibitors MD treatment (prasugrel is not allowed). Prior to any and all study-specific examinations, subjects will be informed as to the extent and nature of their study participation and will be given the opportunity to provide their written informed consent.

Approximately 10 active study sites in Taiwan will include a total of 200 subjects in order to have at least 170 completed subjects.

Both inclusion and exclusion criteria will be assessed during the screening period (see [Section 8.1](#) and [Section 8.2](#), respectively). Corresponding information should be provided in the eCRF.

## 8.1. Inclusion Criteria

Subjects will be eligible for inclusion into the study only if all of the following criteria are met:

- (1) Subject who has provided signed informed consent.
- (2) Subject of either sex aged  $\geq 20$  years old at the informed consent date
- (3) Subject's weight of at least 50 kg at the time of screening
- (4) Subject with previous diagnosis of ACS (unstable angina [UA], non-ST elevation myocardial infarction [NSTEMI], or ST elevation myocardial infarction [STEMI]) who has undergone PCI and was treated with either:
  - clopidogrel maintenance dose (MD) of 75 mg once daily and aspirin 81-100 mg per day for 2-8 weeks following clopidogrel loading dose (LD) of 300 mg or 600 mg at the time of PCI
  - or ticagrelor MD of 90 mg bid and aspirin 81-100 mg per day for 1-4 weeks and switching to clopidogrel maintenance dose (MD) of 75 mg once daily and aspirin 81-100 mg per day for 2-4 weeks (either directly or via clopidogrel loading dose [LD] of 300 mg or 600 mg) following ticagrelor LD of 180 mg at the time of PCI
  - or clopidogrel maintenance dose (MD) 75 mg once daily and aspirin 81-100 mg per day for 2-8 weeks following ticagrelor LD of 180 mg at the time of PCI

- or based on investigator's judgement with at least 2 weeks continues use of clopidogrel MD and aspirin 81-100 mg per day before switching to prasugrel and maximum 8 weeks P2Y12 inhibitors MD treatment (prasugrel is not allowed)

## 8.2. Exclusion Criteria

A subject will not be eligible for inclusion in this study if any of the following criteria are met:

- (1) Subject with active bleeding or significant increase of risk of hemorrhage such as severe hepatic insufficiency, peptic ulcer present, proliferative diabetic retinopathy, antecedents of severe systemic bleeding, gastrointestinal bleeding, macrohematuria, intraocular hemorrhage, hemorrhagic stroke, or intracranial bleeding), or other antecedents of bleeding diathesis or coagulopathy.
- (2) Subject with any transient ischemic attack [TIA] within 3 months before the informed consent date, or any ischemic stroke within 3 months before the informed consent date, or any previous hemorrhagic stroke.
- (3) Subject with known allergies or hypersensitivity to prasugrel, aspirin, or any of their excipients.
- (4) Subject with significant hypertension (systolic blood pressure > 180 mmHg or diastolic blood pressure > 110 mmHg) at either the time of screening or baseline assessment
- (5) Subject with hemoglobin <10.5 g/dL, or hematocrit < 30% at screening
- (6) Subject with severe left ventricular systolic dysfunction, EF < 35% within 3 months before baseline (visit 2)
- (7) Subject is under hemodialysis
- (8) Subject with evidence of severe hepatic disease, or any of the following: serum alanine transaminase (ALT) or aspartate transaminase (AST)  $\geq$  3 times the upper limit of normal (ULN) laboratory reference range; or bilirubin  $\geq$  2 times the ULN of laboratory reference range at screening.
- (9) Subject with any other results of clinical laboratory tests at the time of screening that are judged by the investigator that could be detrimental to the Subject or could compromise the study
- (10) Female pregnant or of child bearing potential, unless she has a negative serum pregnancy test at screening and agrees to use at least one method of contraception during the study.
- (11) Subject currently enrolled in, or discontinued within the last 30 days prior to baseline from, a clinical study involving an off-label use of an investigational drug or device, or concurrently enrolled in a non-observational clinical study or any other type of medical research judged not to be scientifically or medically compatible with this study.

- (12) Subject who has previously completed or withdrawn from this study.
- (13) Subject with evidence of significant active neuropsychiatric disease, alcohol abuse or drug abuse, in the investigator's opinion
- (14) Subject who is unreliable and unwilling to make him/herself available for the duration of the study and who will not abide by the research unit policy and procedure and study restrictions.

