## 8.4.2 Study Procedures

### Screening assessments (Visit 1, Day -28 to Day -1)

Subjects will be screened for enrolment within 4 weeks prior to the start of prasugrel MD. Subjects will be screened in accordance with predefined entrance criteria as described in [Sections 8.1 and 8.2](#). See [Section 8.5.1](#) for the procedure for documenting screen failures.

Procedures to be completed at screening include:

- Subject information/Informed consent signed and dated.
- Demographics
- Assessment of inclusion / exclusion criteria.
- Medical history and previous medication
- Physical examination
- Vital signs (including blood pressure)
- Laboratory (hematology, biochemistry), serum pregnancy test (for women of childbearing potential)
- Electrocardiogram
- Determination of subject eligibility
- Recording of adverse events

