### Treatment Day 1 (Visit 2)

This visit will be performed on the 1st prasugrel MD administration (Day 1). The following examinations/procedures will be performed:

- Confirmation of inclusion / exclusion criteria.
- Confirmation of subject eligibility
- Physical examination
- Vital signs (including blood pressure)
- Laboratory (platelet function) to be done immediately before first dose of prasugrel MD + aspirin administration of Day 1
- Laboratory (hematology, biochemistry)
- Recording of bleeding events
- Recording of major adverse cardiovascular events
- Recording of all cause death
- Study drug dispensing (prasugrel 3.75 mg)
- Recording of adverse events
- Recording of concomitant medication

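### Exclusion criterion 2 stops looking for TIA and ischemic stroke at consent, up to 28 days before the first prasugrel dose, so a subject with such an event during screening can be dosed

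*Combined protocol and SAP*

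**What the plan says.** Criterion 2 in section 8.2, repeated in the Summary, has three limbs: TIA ("Subject with any transient ischemic attack [TIA] within 3 months before the informed consent date"), ischemic stroke ("any ischemic stroke within 3 months before the informed consent date") and hemorrhagic stroke ("or any previous hemorrhagic stroke"). Only the first two are dated from consent.

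On timing, section 7.1 puts consent first: "After signing the study informed consent, subjects will enter a flexible screening period based on the investigator's discretion (lasting up to a maximum of 4" (the unit is weeks). Section 8.4.2 agrees: "Subjects will be screened for enrolment within 4 weeks prior to the start of prasugrel MD". Appendix 18.1 shows screening as Day -28 to Day -1. The Day 1 list in section 8.4.2 includes "Confirmation of inclusion / exclusion criteria", and Appendix 18.1 marks the criteria at both Visit 1 and Visit 2.

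Three other exclusions in the same list reach baseline. Criterion 4 (blood pressure) applies "at either the time of screening or baseline assessment". Criterion 6 applies to "EF < 35% within 3 months before baseline (visit 2"). Criterion 11 counts its 30 days back from baseline.

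Section 11.1.1 defines the safety population (SAF) as everyone given at least one dose, and the per-protocol (PP) set as SAF subjects without a major deviation. Section 10.1 counts violation of an entry criterion as a major deviation.

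**The concern.** Subjects are in the weeks after an acute coronary syndrome and PCI, on dual antiplatelet therapy, and events can occur during screening. A criterion that looks back only from consent cannot see them. It therefore excludes some older events and passes over the most recent ones, and the protocol gives no reason for doing so.

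The first stake is subject protection: a TIA or ischemic stroke shortly before the first dose is not a mandatory exclusion. The second is the make-up of the cohort. Non-fatal stroke is a MACE component and major bleeding is the Period 2 primary endpoint (section 6.2.2). The study has no control group to show whether a later event reflects the earlier illness.

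**Working it through.** **Step 1: the anchors side by side.**

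| Exclusion | Period covered | Reaches Day 1? |
|---|---|---|
| 2, TIA | 3 months back from consent | No |
| 2, ischemic stroke | 3 months back from consent | No |
| 2, hemorrhagic stroke | any earlier time | Yes |
| 4, blood pressure | screening or baseline | Yes |
| 6, ejection fraction | 3 months back from baseline | Yes |
| 11, other studies | 30 days back from baseline | Yes |

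The uncovered interval for TIA and ischemic stroke runs from consent to Day 1, up to 28 days.

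**Step 2: two subjects at the Day 1 confirmation.** Suppose consent is on Day -20 and take 3 months as about 91 days.
- Ischemic stroke 89 days before consent: about 89 + 20 = 109 days before the first dose. It is inside the window, so the subject is excluded.
- Ischemic stroke on Day -10: about 10 days before the first dose and 10 days after consent. It is not before consent, so criterion 2 is not met.

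Repeating the check on Day 1 changes neither answer, because the text being checked is the same.

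**Step 3: do the analysis sets catch it?** The second subject, once dosed, is in the SAF. Criterion 2 was satisfied as written, so there is no entry violation on that ground under section 10.1, and the subject can stay in the PP set too.

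**Step 4: how many subjects?** The documents give no TIA or stroke rate for screening, so the rate p over the screening period is an assumption. With 200 enrolled (section 11.2), the expected number is 200p and the chance of at least one is 1 - (1 - p)^200.

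| Assumed p | Expected subjects | Chance of at least one |
|---|---|---|
| 0.1% | 0.2 | 18% |
| 0.25% | 0.5 | 39% |
| 0.5% | 1.0 | 63% |
| 1% | 2.0 | 87% |

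The first three rows are the working range, and the last shows the effect of doubling its top. Screening may be shorter than 28 days, which lowers p.

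**Step 5: does an endpoint move?** Notes 6 and 7 of Appendix 18.1 make an event before the first dose a pre-treatment adverse event. Sections 8.4.1.10 and 8.4.1.11 assess bleeding and deaths only after the first prasugrel dose, and the section 6.1 objectives run from baseline. An admitted subject adds to an endpoint only by having a further event on treatment. If 5% to 20% did so (again an assumption), the expected excess is 0.2 x 0.05 = 0.01 to 1 x 0.20 = 0.2 events.

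**Step 6: sample size.** Section 11.2 uses a 1% incidence to show that 170 subjects suffice to see at least one event: 1 - 0.99^170 = 0.819, matching its 82%. Nothing in that section depends on criterion 2.

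**The case against.** The strongest reply is that passing one criterion is not the same as being dosed. The Day 1 list has a separate item for confirming eligibility. Adverse events are collected from consent, so a screening stroke would be recorded, and reported within 24 hours if serious. Section 8.5.1 lists an adverse event among the reasons for screen failure. Criterion 1 describes hemorrhage risk through an open list of examples. All of this stands, and it is why the conclusion is that such a subject can enter, not that the subject will. But each of these routes depends on the investigator's judgement, across about 10 sites. None makes a TIA or ischemic stroke in screening a mandatory exclusion.

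A second reply is that anchors before baseline are common here: criteria 5, 8 and 10 rest on screening tests, criterion 9 on screening laboratory results, and inclusion criteria 2 and 3 on consent or screening. That is true, so inconsistency alone does not settle the matter. Those items, however, are values or facts read at one time point, whereas criterion 2 concerns events that can go on occurring until the first dose.

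A reader might also infer that one admitted subject would raise an event percentage by half, from 2 events in 200 to 3. The documents do not support this. The 1% in section 11.2 is an incidence used for a detection statement about adverse reactions or other events in 170 subjects, not an expected rate of MACE or major bleeding in 200. An admitted subject is also not an endpoint event. Even on a base of 2, the 0.01 to 0.2 excess events in step 5 amount to 0.01/2 = 0.5% to 0.2/2 = 10%, on assumed rates throughout.

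**Conclusion.** The gap is real on the text. For up to 28 days between consent and Day 1, criterion 2 does not cover TIA or ischemic stroke, and the Day 1 confirmation does not close the gap. A subject with such an event can be dosed and analysed in both the SAF and the PP set unless the investigator intervenes. Hemorrhagic stroke is outside the point.

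The size is small: probably at most about one subject of 200, on an assumed 0.1% to 0.5% over screening. The documents do not show that prasugrel would be charged with the screening event, or that any endpoint would shift materially. The change in PRU, the Period 1 primary endpoint, has no evident exposure. The case for correction rests on subject protection and on a stated rule that misses the most recent events, at almost no cost to put right.

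**What to change.** In section 8.2 and the Summary, the sponsor should reconcile the anchor of criterion 2 with the criteria that reach baseline and with the Day 1 confirmation, so that a TIA or ischemic stroke between consent and Day 1 is explicitly covered. The existing Day 1 check would then apply to the screening weeks without a new procedure.

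The new wording should extend the covered period and not merely shift it. If the 3-month look-back were simply moved from consent to Visit 2, some subjects now excluded would become eligible. With 28 days of screening, an event 80 days before consent lies 80 + 28 = 108 days before Day 1, beyond about 91 days. The period already excluded before consent should therefore be kept. The length of the clinical window is for the sponsor to decide.

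The cost is one wording change in two places and, on the assumed rates, at most about one additional screen failure. No test, visit, sample-size figure or analysis changes.
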